A challenge to ensuring a continuity of HIV care is that the fragmented health care system is not adapted for a mobile population. Patients considered LTFU actually may have switched facilities on

their own as “silent transfers,” which typically are not recognized due to unlinked data across facilities.^{18–20} This misclassification makes it very difficult to accurately assess the effectiveness of national ART programs. Mobility as a potential barrier to engagement in HIV care has been noted in Kenya,^{21,22} Lesotho,²³ Zambia,²⁴ and the US²⁵. South Africa’s population is highly mobile; the most typical pattern is of circular, within-border migration between rural and urban areas, with the mobile individual keeping strong ties to the rural areas by sending remittances to their family and returning to the rural area for holidays and family events, and upon retirement, illness, or during lapses in employment.²⁶ Postpartum women in South Africa are likely to be a particularly mobile group, due to a tradition of returning to one’s rural home after delivery to receive care from family members.^{12,27,28} Our recent formative work at three sites in Johannesburg found that among 150 peripartum, HIV-positive women interviewed, 44% planned to travel around delivery – typically after delivery – to stay with family, sometimes leaving the infant in the care of family while the mother returned to work in Johannesburg (manuscript under review). HIV-exposed infants – even if HIV-uninfected – are at higher risk of mortality than HIV-unexposed infants²⁹ and require attentive follow-up. With no way of tracking mobility, it is difficult to intervene appropriately to ensure continuity of HIV care for mother and infant.

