Mobility data will be collected throughout the follow-up period. Geospatial coordinates will be recorded with a timestamp. Upon bulk extraction of these data, we will import location information as decimal degree coordinates into ArcMap spatial analysis software. Data charges related to the app are reverse-billed through our app development consultants to ensure timely transmission of data with no cost to participants.

Weekly raffle incentive

To encourage participants to keep the CareConekta app installed on their phone and the GPS function enabled throughout the entire study period, we will offer an incentive: a weekly raffle of one 200MB data bundle (worth approximately \$4). Participants will be eligible to enter the raffle if their phone sent GPS coordinates at least once per day for the prior week. Winners will be randomly selected among all eligible participants using a randomization code automated in STATA. The weekly raffle incentive will only apply to participants enrolled from October 2020 onwards and who have signed version 5.0 or later of the Informed Consent document. There is no limit to the number of times a participant may win the raffle.

Six-month postpartum follow-up visit procedures

Recontacting participant

All participants will be recontacted six months postpartum to return to the study site for a one-time visit. A minimum of three contact attempts by phone and/or home visit will be made for each participant. All contact attempts (successful or not) will be recorded on a contact log.

Follow-up questionnaire

Study staff will complete a face-to-face questionnaire with each participant. This follow-up questionnaire will include reasons for overall acceptability of CareConekta (standard or enhanced), reasons for travel and clinic switching, and barriers and facilitators to care since the start of the study. Response options primarily will be categorical, with open-ended questions to allow for deeper elaboration. Additional questions will be asked of participants in the intervention arm regarding acceptability and feasibility of the intervention. Responses will be recorded directly into a REDCap database by an interviewer using a tablet computer or laptop. This questionnaire may be conducted telephonically.

Viral load testing and potential blood draw

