Electronic and paper files will be reviewed after the participant's final visit to assess engagement in HIV care. If the participant fails to return for a final visit, files will be reviewed a minimum of seven months after estimated delivery. Electronic data on health facility visits and pharmacy dispensing, including facility recorded deaths, will be requested the Provincial Health Data Centre of the Western Cape Department of Health by providing a list of folder numbers of women who have consented and enrolled in the study. These data include all public health facilities in the Western Cape Province, which is the location of the study site. Laboratory records, including viral loads, from any South African facility will be abstracted from the NHLS database. Participants in both arms who are lost from the study at the time of study close will be traced through staff outreach and electronic/paper medical records. Informed consent will include permission to link with electronic medical records.

Table of schedule of measures

Item for completion	Enrolment	Early postpartum phone call	6 months postpartum
Eligibility Checklist	x		
Informed Consent	x		
Linkage form	x	x child details	
Randomisation log	x		
Demographics and medical history	x		x
Maternal mobility (past and planned)	x		x
Maternal clinic switching	x		x
Perceived barriers and facilitators of engagement in care	x		x
Depression (PHQ-4)	x		x
Alcohol and drug use (AUDIT-C and DUDIT Q1)	x		x
Patient provider relationship scale	x		x
ART adherence	x		x
WHO VAW (intimate partner violence)	x		
Social impact scale (stigma)	x		
Availability of social support	x		
Life events (trauma)			x
Infant health			x
Child mobility			x
Acceptability of CareConekta			x
Impact of COVID-19 & lockdown of HIV care and mobility			x
Laboratory tests			
HIV viral load*			x
Record review			
Antenatal and obstetric information	x	x	x
ART pharmacy records	x	x	x
Maternal laboratory results	x	x	x
Child HIV testing		x	x

* If no routine viral load result found in the three months before the study visit

DATA COLLECTION AND STORAGE

Data collection methods

Data will be collected in three ways:

- Face-to-face enrollment and follow-up questionnaires

- Medical record review (electronic and paper file records) to determine participant engagement in HIV care
- Electronic app usage and mobility data

Questionnaire data

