Aim 2b. To evaluate the initial efficacy of the enhanced CareConekta intervention, using notifications and staff contact to improve engagement in HIV care, by assessing the association between study arm and engagement in HIV care at six-months postpartum.

Outcome: Efficacy of the intervention

The overall efficacy analysis will include participants in both arms (n=200). To assess overall cohort engagement in HIV care, we will report retention in care, which will be assessed at the six-month postpartum point and defined as no documented HIV-specific contact with any healthcare facility (including medication pick-ups) for >3 months. We also will report viral suppression six months after delivery based on the viral load test closest to the six-month period, using thresholds of ≤50 and ≤1000 copies/ml. Additionally, we will report vertical HIV transmission and completion of the routine 10-week infant PCR test.

Study arm assignment is the primary exposure of interest. We will use Cox proportional hazard regression models to estimate the association of study arm assignment on these outcomes, and will produce adjusted hazard ratios and 95% confidence intervals for retention in care and achieving viral suppression by study arm. We also will identify other predictors of engagement in HIV care. We will produce crude Kaplan-Meier curves to time to loss to follow-up and time to viral suppression by study arm. In a secondary analysis, we will perform an as-treated analysis using self-reported data regarding actually reading the notifications and/or WhatsApp messages or staff phone calls to analyze the effect of receiving the intervention.

HUMAN SUBJECTS' PROTECTION

Ethical review process

The research protocol will be reviewed by the Institutional Review Boards at Vanderbilt University; the University of California, San Francisco; and the University of Cape Town in South Africa. All research activities will occur in South Africa. All procedures will conform to U.S. and South African ethical standards for human subjects' research.

Informed consent

Informed consent will be obtained for all participants as described in the "Informed Consent" section above.

Privacy and confidentiality

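### Outreach tracing is triggered by loss from the study, not by absence of documented care, so women who complete follow-up while in care outside the Western Cape may be scored lost with no step to confirm their care

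*Combined protocol and SAP*

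**What the plan says.** - **Tracing (File review activities).** "Participants in both arms who are lost from the study at the time of study close will be traced through staff outreach", and through electronic or paper records. The section does not define loss from the study.
- **Outcome (Analysis plan, Aims 1b and 2b).** Retention is assessed at six months postpartum. Its definition is worded as loss: "no documented HIV-specific contact with any healthcare facility (including medication pick-ups) for >3 months".
- **Source for the outcome (Data collection methods).** Engagement is assigned to record review: "Medical record review (electronic and paper file records) to determine participant engagement in HIV care". Questionnaires are listed as a separate source.
- **Reach of the records (File review activities).** All women's files are reviewed. Of the electronic visit and pharmacy data, the section says: "These data include all public health facilities in the Western Cape Province, which is the location of the study site". Laboratory results come from the national NHLS database.
- **Viral load timing (Viral load testing and potential blood draw).** Routine tests are six-monthly during breastfeeding. A woman seen at the follow-up visit with no result in the previous 3 months has blood drawn at the Gugulethu clinic.
- **Six-month contact.** Every woman gets at least three attempts, by phone or home visit. The questionnaire covers clinic switching, and "This questionnaire may be conducted telephonically".

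**The concern.** The tracing trigger and the outcome do not match. Tracing asks whether the study has lost the woman; the outcome asks whether a record shows her in care. A woman who has moved to another province and answers by telephone is, on an ordinary reading, not lost from the study. Her visits and medication pick-ups there lie outside the provincial data. If she has no NHLS result in the window, the definition scores her as lost. Had she not answered, the plan would have traced her.

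The Introduction describes this very problem: silent transfers "which typically are not recognized due to unlinked data across facilities". The error would concentrate in travellers, who are the exposed group in Aim 1b and the women the intervention is designed to reach in Aim 2b. The Study Site section names the Eastern Cape as a usual origin and destination, which is outside the provincial data. In Aim 2b the intervention directs women to clinics near their new location, so its successes may be the care that the records miss. The pilot is meant to guide the size of a later trial and would carry this bias forward.

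**Working it through.** **The plan's own figures.** 4,000 × 0.30 = 1,200 HIV-positive women a year, or 100 a month. 100 × 0.30 = 30 enrolled a month, and 200 / 30 = 6.67, about 7 months. 200 × 0.25 = 50 travellers, or 25 per arm at 1:1. These reproduce. The plan gives no power calculation and no figure tied to tracing.

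**Inputs for the illustration.**
- L, true loss: 25% and 48%, rounded from the 25.2% (one year, women pregnant at ART initiation) and 47.9% (within six months of delivery) in the Introduction. Applying them here is an assumption.
- g, share of in-care travellers who are in care only outside the province and answer the questionnaire: 0.1 to 0.5, assumed.
- u, share of those with no NHLS result in the 3-month window: 0.5 to 1.0, assumed. With one test every 6 months at uniform timing, 3/6 = 0.5 have a result in the window, so u = 1 − 0.5 = 0.5.

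**Women wrongly scored lost, per arm** = 25 × (1 − L) × g × u.

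**Apparent loss in travellers** = L + (1 − L) × g × u. The ratio divides this by L, that is, with no true mobility effect.

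| L | g | u | Women per arm | Apparent loss | Ratio |
|---|---|---|---|---|---|
| 25% | 0.1 | 0.5 | 0.9 | 28.75% | 1.15 |
| 25% | 0.3 | 0.5 | 2.8 | 36.25% | 1.45 |
| 25% | 0.5 | 1.0 | 9.4 | 62.5% | 2.5 |
| 48% | 0.1 | 0.5 | 0.7 | 50.6% | 1.05 |
| 48% | 0.5 | 1.0 | 6.5 | 74% | 1.54 |

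Example, second row: 25 × 0.75 × 0.3 × 0.5 = 2.8; 0.25 + 0.75 × 0.15 = 0.3625; 0.3625 / 0.25 = 1.45.

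**Aim 2b, one scenario.** Assume 25% loss in non-travellers and 48% in control travellers, an intervention that links half of the lost travellers to out-of-province care, and no other misclassification.
- Control: 0.75 × 0.25 + 0.25 × 0.48 = 30.75%.
- Intervention, true: 0.75 × 0.25 + 0.25 × 0.24 = 24.75%. True difference: 6.0 points.
- Intervention, observed at u = 0.5: 0.75 × 0.25 + 0.25 × (0.24 + 0.24 × 0.5) = 27.75%. Observed difference: 3.0 points.
- At u = 1 the observed difference is 0.

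**The case against.** The best defence is that the plan already reaches these women. "Electronic and paper files will be reviewed after the participant's final visit to assess engagement in HIV care", so record review is not confined to women lost from the study. Care at another Western Cape public facility is captured, and NHLS results are national. All women get repeated contact attempts at six months, and those who answer are asked about clinic switching. Those who attend in person without a recent viral load have blood drawn. A trip of more than 50 km for more than 7 days may be short or stay within the province, whereas a false loss needs more than 3 months without a recorded contact.

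All of this stands, and it rules out one reading that a reader might infer: that women in care elsewhere who answer are never traced and are always scored lost. Some will be picked up by the records. What remains is a missing rule. The plan does not say that a reported clinic is contacted, or whether a reported switch, an NHLS result or the study blood draw counts as documented contact. A telephone respondent does not get that draw by answering.

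A reader might also infer that tracing waits until study close, so that the delay varies with enrolment date by about 200 / 30 = 6.7 months. The phrase may equally describe when loss is judged, and the documents do not show that delay would alter an outcome read from dated records at a fixed point. The span also uses only the planned rate.

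Finally, tracing applies to both arms and the plan disclaims adequate power for Aim 2b. That limits claims about significance, but it does not remove bias in the estimate.

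**Conclusion.** The concern holds as a gap in outcome ascertainment. Women who complete follow-up, have no documented contact in the window and are in care outside the Western Cape may be misclassified as lost, because tracing is not keyed to the outcome. The likely direction is to exaggerate harm from mobility in Aim 1b and to understate benefit in Aim 2b if the intervention links women to care elsewhere.

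The size is unknown. The illustration gives 0.7 to 9.4 women per arm of 100, with 2.8 at L = 25%, g = 0.3 and u = 0.5; g and u are assumptions, and so is applying the quoted loss rates to this cohort. A reader might infer a larger toll by supposing that 40% of the 50 travellers (20 women) are in care that no record shows, that 60% of them answer and so go untraced, and that tracing resolves 70% of the rest: 12 + 8 × 0.3 = 14.4 women, or 29% of travellers. The arithmetic is right, but the documents do not support those inputs. The change should be made, because it is specific and cheap.

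**What to change.** Keep the existing tracing sentence, since viral suppression and the infant outcomes also depend on tracing women lost from the study. Add after it:

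*In addition, any woman in either arm whose file review shows no documented HIV-specific contact in the 3 months before her six-month point will be traced at her own file review, whether or not she was interviewed, starting from any clinic switch she reported; facility and contact dates up to six months postpartum will be confirmed with that facility where possible.*

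In the analysis plan for Aims 1b and 2b, state whether each of these counts as contact: an NHLS result, the study blood draw, and self-reported care that could not be confirmed. Report a sensitivity analysis that counts self-reported care elsewhere as retained.

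The cost is a protocol amendment, some additional contacts with women who have already taken part, and record checks with facilities outside the province. Existing staff can do this: outreach is already planned, and women who answered are already reachable. The facility checks are new work, and some will not succeed.

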	Q1	Q2	Q3	Q4	Q1	Q2	Q3	Q4	Q1	Q2	Q3	Q4
Study preparation												
IRB approval and renewal												
ClinicalTrials.gov registration												
Develop study instruments and REDCap database												
Adapt CareConekta smartphone app												
Confirm eligibility, recruit and consent participants												
Enrollment questionnaire												
Participant follow-up												
Follow-up questionnaire												
File review												
Data analysis												
Manuscript preparation												
R01 submission and revision												

STUDY DESIGN

Sample Size

We will enroll 200 participants.

For this pilot trial formal sample size estimation was not conducted. The sample size was reached based on the feasible enrolment from the study site within the study timeline. Approximately 4,000 women seek antenatal care at the MOU annually; ~30% of these are HIV-positive, about 1 200 per year, or 100 per month. Our formative work (HREC REF 792/2016 and 227/2017) showed that over half of these women own smartphones. If we conservatively estimate that 30% of all pregnant, HIV-positive women seeking antenatal care each month will be eligible and interested which equals 30 participants enrolled per month. We anticipate that it will take approximately seven months to reach our enrolment target of 200 participants (see Timeline above).

Based on our earlier work in South Africa and at the study site, we estimate that 25% of the participants will engage in long-distance travel during the study period. A sample size of 200 allows us to characterize the mobility experiences of 50 women who travel and explore differences with those who do not. While we do not anticipate having sufficient power to detect statistically significant differences between groups in Aims 2b, the information gained through this pilot study will inform sample sizes for larger future studies should this pilot show promise.

Study arms

- **Control arm (n=100):** Participants will receive standard CareConekta, which will track their mobility and allow the participant to look up new ART facilities upon request.
- **Intervention arm (n=100):** Participants will receive standard CareConekta with the following additions:
 - text notifications of nearby ART facilities when they have traveled >50 km from the study site for >7 days

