In routine care in this setting, viral load tests are to be repeated every three months in pregnancy and every six months during breastfeeding, so we expect that most women will have a routine viral load completed before six months postpartum. To avoid additional blood draws for the participant, at the follow-up visit, the study staff will check NHLS to determine the most recent viral load test. If the participant has had no viral load test within 3 months prior to the six-month study follow-up visit, a blood draw for viral load will be conducted by the clinical staff at the Gugulethu CHC. A clinic nurse will collect 5 ml of venous blood, which will be transported daily to the National Health Laboratory Services (NHLs) for HIV viral load testing (Abbott Molecular RealTime HIV-1 assay (Abbott Molecular, Illinois, USA). We will not recontact participants about viral load results unless participants are on ART and the viral load result indicates lack of viral suppression. In that case, results will be made available to participants over the phone (or in person, at participant's wish) with appropriate referrals. For all participants, viral load results will be captured using the participants provincial folder number into the NHLs database, as is standard practice for routine laboratory results in South Africa.

Uninstall app

During the follow-up visit, the CareConekta app will be uninstalled from each participant's phone.

Reimbursement

After all the above steps are complete, the enrollment visit will conclude with providing the participant R150 reimbursement for transport and missed opportunity costs. Payment will be made in cash and/or grocery vouchers and will be recorded in a reimbursement log.

File review activities

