Aim 1a. To use GPS location data from CareConekta and spatial analysis to characterize peripartum mobility within the complete observational cohort (n=200), including the frequency, distance, and timing.

Outcome: Mobility within the study period

We will use data from all 200 participants to describe mobility within a complete observational cohort. In order to assess mobility comprehensively, we will use multiple data sources: time- and date-stamp data as well as geographic location data from CareConekta, participant self-report during questionnaires, and electronic medical records during the file review. Participant questionnaire data and medical record data will be exported from REDCap, and mobility data from CareConekta will be imported from .csv files to SAS for data analysis. To assess the primary outcome of interest, we will report the number of participants who travel during the study period (defined as >50 km for >7 days), over the denominator of all participants. Among those who travel, we will report the median and interquartile range number of trips during the study period and will determine timing and

frequency of travel as it relates to delivery date, which will be obtained from participant questionnaire and/or medical records. Median and interquartile range duration of travel will be reported in days, and we will also assess temporicity (frequency of trips x duration of trips). Reasons for travel will be obtained from the enrollment and follow-up questionnaire and will be grouped by theme, such as family, work, housing, and education.

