To assess engagement in HIV care, we will report retention in care, which will be assessed at the six-month postpartum point and defined as no documented HIV-specific contact with any healthcare facility (including medication pick-ups) for >3 months. We also will report viral suppression six months after delivery, using thresholds of ≤ 50 and ≤ 1000 copies/ml. Additionally, we will report vertical HIV transmission and completion of the routine 10-week infant PCR test.

We will fit a series of models of mobility metrics on outcomes. For one, we will use a dichotomous exposure of mobility (any travel >50 km: yes/no), we will use Cox proportional hazard regression models to estimate the association of mobility on these outcomes, and will produce adjusted hazard ratios and 95% confidence intervals for retention in care and achieving viral suppression. We also will identify other predictors of engagement in HIV care. We will produce crude Kaplan-Meier curves to time to loss to follow-up and time to viral suppression by mobility group. Additionally, we will perform sensitivity analyses to explore how the estimated effect size changes when using varying cut-off points to define mobility.

Aim 2a. To assess the acceptability and feasibility of the standard and enhanced app, with a focus on identifying user preference and implementation outcomes.

Outcome: Acceptability and feasibility of CareConekta

Acceptability and feasibility data will be collected among all 200 participants. Those in the intervention arm will receive additional questions related to the enhanced app features. The outcomes selected for analysis in Aim 3a correspond with the Technology Acceptance Model for Resource-Limited Settings (TAM-RLS) framework, which was designed to draw attention to end-user acceptability as a predictor of mHealth technology adoption in low-resource settings.⁴⁶ We will report proportions and 95% confidence intervals for categorical variables and medians and interquartile ranges for continuous variables. For open-ended questions, we will create a list of categorical themes that emerge over multiple readings and calculate the proportions for the response categories. We will select key illustrative quotes for each theme.

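### Aim 1a divides observed travellers by all women, whatever was observed of each, so uncaptured travel is reported as no travel; the same error can weaken the Aim 1b association

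*Combined protocol and SAP*

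**What the plan says.** Under Analysis Plan and Study Outcomes, Aim 1a, the primary mobility outcome is "the number of participants who travel during the study period (defined as >50 km for >7 days), over the denominator of all participants". That section treats the 200 women as a fully observed cohort. It names three sources of mobility data: the app, the questionnaires and the electronic medical records.

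Aim 1b is restricted to the control arm. For one of its models, "we will use a dichotomous exposure of mobility (any travel >50 km: yes/no", so it has no level for unknown mobility and, unlike Aim 1a, no 7-day condition. The only sensitivity analysis planned for mobility varies the cut-off.

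Loss of app data is foreseen. The Weekly raffle incentive section sets up a prize draw "To encourage participants to keep the CareConekta app installed on their phone and the GPS function enabled throughout the entire study period". The draw covers only women enrolled from October 2020 who signed version 5.0 or later of the consent form. On the end of tracking, the Uninstall app section says: "During the follow-up visit, the CareConekta app will be uninstalled from each" participant's phone. The Follow-up questionnaire section allows that interview to be done by telephone.

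The Sample Size section gives the planning figure: "we estimate that 25% of the participants will engage in long-distance travel during the study period", and "A sample size of 200 allows us to characterize the mobility experiences of 50 women who travel".

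**The concern.** A proportion over all participants is sound only if every participant's status is known. Here follow-up runs to about nine months on the woman's own phone, and the app can be removed or GPS switched off at any point. Under the stated denominator, a woman with no captured mobility data has the same effect as a woman who stayed at home. The plan has no observed time, coverage threshold, source ranking or unknown category that would separate the two.

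Aim 1a's headline figure describes how common peripartum travel is, and a later trial would plan on it. In Aim 1b the error may be tied to the outcome: a woman who leaves the area may lose the app, miss the interview and drop out of the records together. She would then be labelled not mobile and lost from care, which moves a lost woman from the exposed to the unexposed group.

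**Working it through.** **Inputs.** From the protocol: 200 women, 25% expected to travel, 50 travellers, nine months of follow-up, 100 women in the control arm. The documents give no rate of app loss or missed interview, and no risk of loss from care by mobility group for this trial. Every such value below is an assumption.

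**1. The plan's own figure.** 200 × 0.25 = 50 travellers, as stated.

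**2. A share u of women unobserved, unrelated to travel; true proportion 25%.**
Planned figure = 50(1 − u)/200. Known-status figure = 50(1 − u)/[200(1 − u)]. Upper bound, with all unknowns counted as travellers = [50(1 − u) + 200u]/200. The lower bound equals the planned figure.

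| u | Observed travellers | Planned figure | Known status only | Bounds |
|---|---|---|---|---|
| 10% | 45 | 22.5% | 25% | 22.5–32.5% |
| 20% | 40 | 20% | 25% | 20–40% |
| 30% | 35 | 17.5% | 25% | 17.5–47.5% |
| 40% | 30 | 15% | 25% | 15–55% |

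**3. Travellers unobserved more often (50% v 20%).** Observed travellers: 50 × 0.5 = 25. Women with known status: 25 + 150 × 0.8 = 145. The planned figure is 25/200 = 12.5% and the known-status figure 25/145 = 17.2%. With 55 unknown, the upper bound is (25 + 55)/200 = 40%. Changing the denominator alone therefore does not remove the bias; only the bounds contain the true 25%.

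**4. Partial transmission, with the app as the only source.** Assume constant hazards, with λ = −ln(0.75)/9 per month for a first trip and μ = −ln(S)/9 for app loss, where S is the share still transmitting at nine months. The observed proportion is λ/(λ + μ) × (1 − 0.75S). For S = 90%, 75%, 50% and 25% it is 23.8%, 21.9%, 18.3% and 14.0%, or 47.6, 43.8, 36.7 and 27.9 women instead of 50. Interviews and records would recover some of these.

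**5. Aim 1b.** A 2×2 table stands in for the planned Cox model. Assume 25 travellers and 75 others among 100 controls, with risk of loss from care 50% v 25%: 12.5 and 18.75 lost, true risk ratio 2.0. Unobserved travellers are moved to the unexposed group. Worked row, mobility unobserved in 40% of lost and 10% of retained women:

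- Labelled travellers: 12.5 × 0.6 = 7.5 lost and 12.5 × 0.9 = 11.25 retained; risk 7.5/18.75 = 40.0%.
- Labelled non-travellers: 18.75 + 5 = 23.75 lost and 56.25 + 1.25 = 57.5 retained; risk 23.75/81.25 = 29.2%.
- Risk ratio 1.37.

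| Unobserved: lost / retained | Risk ratio (50% v 25%) | Risk ratio (40% v 20%) |
|---|---|---|
| 0 / 0 | 2.00 | 2.00 |
| 20% / 5% | 1.68 | 1.64 |
| 30% / 30% | 1.83 | 1.83 |
| 40% / 10% | 1.37 | 1.30 |
| 60% / 10% | 0.98 | 0.90 |
| 80% / 10% | 0.55 | 0.47 |

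Weakening is the usual result. Erasure needs a contrast of about 60% v 10%.

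**The case against.** The plan does not rely on the app alone. Aim 1a names self-report and medical records as well. All women are to be telephoned about a week after the expected delivery date and asked where they are. The six-month contact allows at least three attempts by phone or home visit, an alternative contact may be held, laboratory records are national, and women lost from the study are traced at its close. Nor does any sentence say that a woman with unknown mobility is to be coded as a non-traveller. Mobility is also a secondary objective, Aim 1b is exploratory, and "For this pilot trial formal sample size estimation was not conducted".

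Much of this stands, and it makes the gap smaller than app loss alone would suggest. It does not close the gap. One location call cannot show a stay of more than seven days, and the schedule of measures lists maternal mobility only at enrolment and six months. Visit and pharmacy records cover the Western Cape, while the Study Site section describes travel to and from the Eastern Cape. Laboratory records exist only for women who were tested, and no mobility measure is given for the tracing step. The coding need not be written down, because the stated denominator produces it for anyone whom these sources miss.

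Two stronger readings are tempting. A reader might infer that the mobility association will be erased. The working does not support that without strongly outcome-dependent missingness. There is also an opposing error: a traveller in care outside the Western Cape may look lost, which would strengthen the association. A reader might also infer that location tracking continues after a woman withdraws. No passage says so, consent pages are not in the text available here, and transmitted positions are randomised within 1 km. What the text does show is narrower: removal of the app is tied to a visit that some women may complete only by telephone or not attend.

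**Conclusion.** The concern holds for Aim 1a. With the stated denominator, travel that no source captures lowers the reported proportion. If the true value is 25%, the report would be 22.5% to 15% when 10% to 40% of women are unobserved regardless of travel, and lower if travellers are missed more often. These shares are assumptions. An undefined end to the window could add late trips and act the other way; that effect cannot be sized from the documents.

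For Aim 1b the supported conclusion is weaker. Misclassification can attenuate the association, and erases it only in extreme patterns of missing data. Western Cape-only visit and pharmacy records may push it upward, so the net direction is uncertain. The 25/75 split used in the working borrows the planning figure for long-distance travel, whereas the Aim 1b exposure is any travel beyond 50 km.

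**What to change.** - **Window.** Define mobility as observed from app installation to six months postpartum, or withdrawal if earlier, and exclude later GPS fixes.
- **Observed time.** Define it per woman across GPS, the six-month interview and records, with a stated rule for combining sources. Keep trips reported after GPS has stopped.
- **Unknown category.** Set a GPS coverage standard; the raffle's once-a-day rule is one candidate. Class women with neither adequate coverage nor another informative source as mobility unknown, in both aims.
- **Reporting for Aim 1a.** Give the number unknown, the proportion among women with known status beside the all-participants figure, and bounds that assign the unknowns both ways. The known-status figure should not stand alone: it can err low, as in step 3, or high, because a trip can be seen on short coverage but its absence cannot.
- **Reporting for Aim 1b.** Repeat the models with the unknowns assigned both ways.
- **Optional sensitivity analysis.** GPS-only time to first trip, censored at last transmission, with a note that the censoring may be informative.
- **Separately.** State a cut-off for GPS collection for women who are not seen in person at follow-up.

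The cost is mainly wording, since timestamps are already stored, plus the collection cut-off. The statistical price is that fewer than 200 women will have known status. If many are unknown, the bounds will be wide: 15% to 55% when 40% are unknown.
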